## 1. Background:

- Shared book reading during the first year of life has been found to have broad developmental benefits for language (Fletcher & Reese, 2005; Karrass & Braungart-Rieker, 2005; Sénéchal & Young, 2008), socio-emotional development (Bus et al. 1997; Xie, et al., 2018), and cognitive abilities ([name] & Monesson, 2009; 2010; [name], 2011; Pickron et al., 2018; Murray & Egan, 2014).
- Previous research suggests that infants exhibit increased attention and perceptual learning and show more specialized brain responses after parents read them books with specifically labeled (individual-level) names for faces or objects from 6- to 9-months of age (Pickron et al., 2018; [name] & Monesson, 2009; 2010; [name], 2011). However, books with generic category labels or no labels have shown no benefit to infant learning under 9 months old.
- One mechanism that may contribute to infant learning from individual-level labels during shared book reading is joint attention. Joint attention is a foundational skill that develops during the first year of life and is important for social learning and language development (e.g, Brooks & Meltzoff, 2005; Tomasello & Farrar, 1986; Mundy et al., 2007).
- The goal of the present investigation is to determine the extent to which increased parent-infant joint attention during shared book reading and across different labeling conditions leads to increases in infant visual selective attention and parent-infant neural synchrony in 6-, 9-, and 12-month-old infants.

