## **2. Specific Aims:**

- Using both eye-tracking and EEG methods, the goal of the present investigation is to (1) determine the extent to which infant and parent visual attentional coupling during shared book reading predicts later: a) infant selective attention and b) infant and parent neural coupling. Specific aim (2) is to determine the extent to which books with individually-named characters (e.g., “Boris”, “Fiona”) increases parent-infant joint attention and infant selective attention relative to books with generic labels (e.g., “Bear”, “Bear”) or no labels and whether attention differs by age.

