## **3. Research Plan / Study Description:**

- A parent of the participant will first be asked to complete short questionnaires before coming into the lab. Often infants have a limited attention span so we have parents fill out the questionnaire consent form and online Qualtrics questionnaire prior to coming in to the lab so we can expedite their time spent in the lab. This keeps the infant content and not fussy so ultimately, we can get better data when the experiment begins. This questionnaire is designed to provide us with demographic information about who has participated in our studies. These questionnaires include questions regarding their child’s gender, race and ethnicity as well as questions about the demographics of their family (see attached Child and Parent Demographic questionnaires). This information is voluntary and confidential to the extent provided by law.
- **Day 1:** Parents will read a book to their infants in a small in-lab playroom, as they would at home. Prior to reading, infants and their parent will be fitted with a Positive Science head mounted eye-tracker. In addition, both audio and video recordings of the book reading session will be collected using a table-mounted camera. Books with six different characters, one on each of 6 pages will be used during shared book reading. Two of the characters will be labeled with individual level names (e.g., “Boris”, “Anis”), two will be labeled with the same category-level name (e.g., “Cow”) and two will not be labeled. Parents will be seated on the floor with their infant or next to their infant in a high chair. See figure below for outcome measures and time frame for experiments.
- **Day 2:** The participants will return a second day to complete the EEG portion of the experiment. The infant and parent participants will view pictures of faces and/or objects presented with or without sounds while their brain electrical activity (EEG) is recorded in the lab. Here, we employ a “flicker” task and recordings of steady-state visual evoked potentials (ssVEPs) as an index of infant visual selective attention. We will examine the ssVEP power evoked by two overlapping visual objects to quantify the degree of visual attention devoted to learned characters relative to novel characters across labeling conditions. Infants and parents will view ten 6-second trials of two overlapping familiar (from the

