book) and unfamiliar characters including the following: 1) Individual-labels: familiar vs. unfamiliar; 2) Category/generic labels: familiar vs. unfamiliar; 3) No labels: familiar vs. unfamiliar

- **Day 2:** For a second EEG recording, we will measure both parent and infant EEG. This time we will be looking for EEG synchrony between the parent and infant by using a similar ssVEP frequency tagging task as above, now using a phase-locking index.
- To record brain electrical activity, a net with recording sensors is placed on the infant's head. In order to help the electrodes accurately measure the infant's brain activity, we will soak this sensor net in an electrolyte solution. The solution contains distilled water, potassium chloride (salt), and baby shampoo. Recording EEG simply picks up the brain activity that is naturally emitted from the scalp and is non-invasive. If the infant does not like wearing the net or is too tired to complete all of these tasks, the family may be asked to return to the laboratory for an additional visit.
- Outcome measures and time frame:

| Type      | Name                            | Time Frame                                      | Brief Description  |
|-----------|---------------------------------|---|--|
| Primary   | Infant Visual Fixations         | On Day 1  | Infant visual fixations will be recorded during shared book reading and duration of attention and joint attention calculated. Three age groups will be examined (6, 9, 12, month olds).                                      |
| Secondary | Parent Visual Fixations         | when their infant is 6-, 9-, 12-months on day 1 | In the lab, parent visual attention will be measured across conditions using a head mounted eye-tracker. Duration of joint attention within a spatial window will be calculated in conjunction with infant visual fixations. |
| Primary   | Infant EEG power                | On Day 2  | Infant EEG power will be measured and compared across conditions and ages.   |
| Secondary | Infant and parent EEG synchrony | On Day 2  | Infant and parent EEG synchrony will be quantified and compared across conditions.   |

- During the study, the parent will be present and near the infant at all times during each session. If the infant fusses or cries and does not wish to look at the pictures and/or read the book, we will take breaks or stop the test. If, at any point or for any reason, the participant family wishes to stop the test they may advise us to stop

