## **6. How the Sample Size is Determined:**

- Power, effect-sizes, and retention rates from [name]'s previous EEG investigations were used to estimate samples sizes. we conducted two power analyses using G\*Power (Faul, Erdfelder, Buchner, & Lang, 2009).
- First, assuming a repeated-measures ANOVA with within-subject factors of character label (individual label, generic label, control) and between-subject factors of age(6-, 9-, 12-months) and a medium effect size of  $d = 0.3$  and power of .80 each group should consist of at least 39 participants. Second, for regression analyses, the power analysis was focused on whether parent infant joint attention scores predicted infant learning (as measured by ssVEP power).
- With a medium effect size of  $f^2 = .15$  (Cohen, 1988) and power of .80, the sample should include 55 subjects.
- Given that we plan to collapse across age for this analysis, our estimated sample size of 60 per age group should be sufficient. In addition, we expect a 70% retention rate based on previous cross-sectional infant EEG investigations conducted in [name]'s laboratory and so recruiting 60 per age groups should allow for both analyses to be well powered.

---

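### The Background goal is worded as a causal effect of joint attention across label conditions, but joint attention is only observed, and the one analysis described for it gives a between-infant association pooled over age

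*Protocol*

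**What the plan says.** **Goal.** Protocol section 1 (Background) asks how far "increased parent-infant joint attention during shared book reading and across different labeling conditions leads to increases in infant visual selective attention" and parent-infant neural synchrony at 6, 9 and 12 months. The same section presents joint attention as a possible mechanism for learning from individual-level labels, and as a skill that emerges over the first year.

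**Aims.** Section 2 puts Aim 1 more modestly: how far "infant and parent visual attentional coupling during shared book reading predicts later" infant selective attention and neural coupling. Aim 2 asks whether individual names raise both joint attention and selective attention relative to generic or no labels.

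**Design.** In section 3 every infant sees all label types: "Two of the characters will be labeled with individual level names", two share a category name and two have no label. Joint attention is not assigned: "Parents will read a book to their infants in a small in-lab playroom, as they would at home". The outcome table says "Infant visual fixations will be recorded during shared book reading and duration of attention and joint attention calculated". On Day 2, ssVEP power is recorded for familiar versus unfamiliar characters under each label type.

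**Analysis.** Section 6 says that "the power analysis was focused on whether parent infant joint attention scores predicted infant learning (as measured by ssVEP power"). It takes f² = 0.15 and power 0.80, arrives at 55 subjects, and plans to pool the age groups for this regression. It recruits 60 dyads per age and expects 70% retention.

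**The concern.** The goal and Aim 1 are different claims. The goal is about an effect of joint attention and refers to differences across label conditions. Aim 1 is about prediction. A regression with one joint-attention score and one ssVEP value per infant answers a third question: whether dyads with more joint attention also have infants with higher ssVEP power.

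Two things could produce that slope without any effect of joint attention:

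- **Stable dyad traits**, such as infant temperament, parental engagement or reading habits at home, which may raise both measures.
- **Age.** The protocol itself says joint attention is developing over this period, and it compares EEG power across ages. If both measures rise with age, pooling 6-, 9- and 12-month-olds creates a correlation.

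The slope also does not show whether, for a given infant, the label condition that drew more joint attention is the one with more selective attention later. That is the across-condition part of the goal. At stake is the study's main sentence about joint attention: a positive regression, read against section 1, would be reported as an effect.

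**Working it through.** **1. Reproduce the plan's figure.** Inputs from section 6: f² = 0.15, power 0.80. Alpha is not stated and is taken as 0.05. For one tested predictor, the noncentral F test has λ = f² × N with 1 and N − 2 degrees of freedom. At N = 55, λ = 0.15 × 55 = 8.25 and power is 0.805; at N = 54 it is 0.798. So 55 reproduces, with one row per subject. It stays 55 with up to six predictors in the model if only one is tested.

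**2. Expected sample.** 3 × 60 = 180 dyads; 0.70 × 180 = 126 retained. Power at f² = 0.15 is then 0.99. There is no shortfall for the association.

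**3. Stable trait, no effect of joint attention.** Let one unmeasured trait correlate a with joint attention and a with ssVEP power (assumed; the documents give no value). The induced correlation is r = a × a. By Fisher's z, the probability of p < 0.05 (two-sided) is about Φ(atanh(r)·√(n − 3) − 1.96), plus a small opposite tail. For a = 0.5 and n = 126: r = 0.25, atanh(r) = 0.2554, × √123 = 2.83, and Φ(0.87) = 0.81.

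| a with each measure | induced r | n = 126 | n = 55 |
|---|---|---|---|
| 0.5 | 0.25 | 81% | 45% |
| 0.4 | 0.16 | 43% | 21% |
| 0.3 | 0.09 | 17% | 10% |
| 0.2 | 0.04 | 7% | 6% |

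The planned effect f² = 0.15 means R² = 0.15/1.15 = 0.130 and r = 0.36. A trait correlated 0.60 with both measures would produce all of it (0.60 × 0.60 = 0.36). A larger sample makes the spurious slope easier to detect.

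**4. Age, no effect of joint attention.** Take 42 infants per age, with both measures rising d within-age SDs per age step (assumed). The age means −d, 0, d have variance 2d²/3, so the pooled correlation is r = (2d²/3)/(1 + 2d²/3), if age is not in the model.

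| d per age step | pooled r | significant, n = 126 |
|---|---|---|
| 0.3 | 0.06 | 10% |
| 0.5 | 0.14 | 36% |
| 0.8 | 0.30 | 93% |

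Simulation agrees to within about two percentage points.

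**5. Does a within-infant slope remove the trait?** Simulation with 126 infants, three conditions each, and only a stable trait correlated 0.5 with every condition-level measure. The within-infant slope, with label condition in the model, is significant in 5% of studies, the nominal rate. The slope on infant means is significant in essentially all.

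**The case against.** **The operative text is already associational.** Aim 1 and section 6 both speak of prediction, and the causal verb sits in the Background. This stands in part: the remedy for the goal is wording. But the goal is where a reader looks for what the study may conclude, and it claims more than Aim 1.

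**Section 6 is a sample-size section.** A subject count in a power calculation does not prove that the final model has one averaged score per infant, or that it omits label and age; a separate SAP may add them. This also stands in part. Still, section 6 states the pooling over age and is the only account of the joint-attention analysis. No SAP can turn an observed score into an assigned one.

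**The labels are manipulated and are meant to shift joint attention.** True, but Aim 2 expects labels to raise selective attention too, so a label effect cannot be credited to joint attention.

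**The bias figures rest on chosen inputs.** This stands. At 0.2 the false-positive rate is close to nominal. If the outcome is the familiar-versus-unfamiliar difference, a trait that lifts both responses equally cancels.

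**Stronger readings that the documents do not support.** A reader might infer that no increase is measured because there is no EEG before reading. The familiar-versus-unfamiliar contrast and the no-label and generic-label conditions are comparators within the infant, so an increase relative to them is measured. A reader might also infer that sizing on subjects is a fault. The figure reproduces, and the expected sample exceeds it.

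**Conclusion.** The goal in section 1 claims more than the design and the one described joint-attention analysis can support. Joint attention is observed, so no regression on it alone establishes an effect. As sized and pooled, the regression implies a between-infant association that stable dyad traits and age can confound, and it leaves the across-condition part of the goal unanswered.

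The size of the bias cannot be determined from the documents. With 126 retained dyads and no effect, the false-positive rate runs from 7% to 81% for assumed trait correlations of 0.2 to 0.5, and from 10% to 93% for assumed age trends of 0.3 to 0.8 SD per step when age is not modelled. These figures assume alpha 0.05, 70% retention and, for the trait, equal correlation with both measures.

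The label comparisons in Aim 2 are not affected. This is a worthwhile, low-cost improvement and not a defect in the sample size.

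**What to change.** 1. In section 1, replace the causal phrase (*leads to increases in*) with *is associated with*, so that the goal agrees with Aim 1.
2. For the joint-attention question, specify one mixed model on condition-level data: Day 1 joint attention and the Day 2 familiar-versus-unfamiliar ssVEP contrast for each label condition in each infant. Split joint attention into the infant's mean and the deviation from it, and include label condition and age group as terms. Use the same model for the synchrony index where it is available by condition.
3. Report the within-infant slope as the across-condition association. It is free of traits that are constant across conditions, but it is not causal: interest in a particular character, for example, can still move both measures. Report the between-infant slope separately, also as association.

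**Cost.** Wording and analysis only, with no new data. The within-infant slope rests on three conditions per infant and is less precise. Its power cannot be computed from the documents, which give no within-dyad correlation. Having label condition in the model also removes the average shift in joint attention that the labels produce. The conclusion becomes weaker.

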## **2. Specific Aims:**

- Using both eye-tracking and EEG methods, the goal of the present investigation is to (1) determine the extent to which infant and parent visual attentional coupling during shared book reading predicts later: a) infant selective attention and b) infant and parent neural coupling. Specific aim (2) is to determine the extent to which books with individually-named characters (e.g., “Boris”, “Fiona”) increases parent-infant joint attention and infant selective attention relative to books with generic labels (e.g., “Bear”, “Bear”) or no labels and whether attention differs by age.

## **3. Research Plan / Study Description:**

- A parent of the participant will first be asked to complete short questionnaires before coming into the lab. Often infants have a limited attention span so we have parents fill out the questionnaire consent form and online Qualtrics questionnaire prior to coming in to the lab so we can expedite their time spent in the lab. This keeps the infant content and not fussy so ultimately, we can get better data when the experiment begins. This questionnaire is designed to provide us with demographic information about who has participated in our studies. These questionnaires include questions regarding their child’s gender, race and ethnicity as well as questions about the demographics of their family (see attached Child and Parent Demographic questionnaires). This information is voluntary and confidential to the extent provided by law.
- **Day 1:** Parents will read a book to their infants in a small in-lab playroom, as they would at home. Prior to reading, infants and their parent will be fitted with a Positive Science head mounted eye-tracker. In addition, both audio and video recordings of the book reading session will be collected using a table-mounted camera. Books with six different characters, one on each of 6 pages will be used during shared book reading. Two of the characters will be labeled with individual level names (e.g., “Boris”, “Anis”), two will be labeled with the same category-level name (e.g., “Cow”) and two will not be labeled. Parents will be seated on the floor with their infant or next to their infant in a high chair. See figure below for outcome measures and time frame for experiments.
- **Day 2:** The participants will return a second day to complete the EEG portion of the experiment. The infant and parent participants will view pictures of faces and/or objects presented with or without sounds while their brain electrical activity (EEG) is recorded in the lab. Here, we employ a “flicker” task and recordings of steady-state visual evoked potentials (ssVEPs) as an index of infant visual selective attention. We will examine the ssVEP power evoked by two overlapping visual objects to quantify the degree of visual attention devoted to learned characters relative to novel characters across labeling conditions. Infants and parents will view ten 6-second trials of two overlapping familiar (from the

book) and unfamiliar characters including the following: 1) Individual-labels: familiar vs. unfamiliar; 2) Category/generic labels: familiar vs. unfamiliar; 3) No labels: familiar vs. unfamiliar

- **Day 2:** For a second EEG recording, we will measure both parent and infant EEG. This time we will be looking for EEG synchrony between the parent and infant by using a similar ssVEP frequency tagging task as above, now using a phase-locking index.
- To record brain electrical activity, a net with recording sensors is placed on the infant's head. In order to help the electrodes accurately measure the infant's brain activity, we will soak this sensor net in an electrolyte solution. The solution contains distilled water, potassium chloride (salt), and baby shampoo. Recording EEG simply picks up the brain activity that is naturally emitted from the scalp and is non-invasive. If the infant does not like wearing the net or is too tired to complete all of these tasks, the family may be asked to return to the laboratory for an additional visit.
- Outcome measures and time frame:

| Type      | Name                            | Time Frame                                      | Brief Description  |
|-----------|---------------------------------|---|--|
| Primary   | Infant Visual Fixations         | On Day 1  | Infant visual fixations will be recorded during shared book reading and duration of attention and joint attention calculated. Three age groups will be examined (6, 9, 12, month olds).                                      |
| Secondary | Parent Visual Fixations         | when their infant is 6-, 9-, 12-months on day 1 | In the lab, parent visual attention will be measured across conditions using a head mounted eye-tracker. Duration of joint attention within a spatial window will be calculated in conjunction with infant visual fixations. |
| Primary   | Infant EEG power                | On Day 2  | Infant EEG power will be measured and compared across conditions and ages.   |
| Secondary | Infant and parent EEG synchrony | On Day 2  | Infant and parent EEG synchrony will be quantified and compared across conditions.   |

- During the study, the parent will be present and near the infant at all times during each session. If the infant fusses or cries and does not wish to look at the pictures and/or read the book, we will take breaks or stop the test. If, at any point or for any reason, the participant family wishes to stop the test they may advise us to stop
- Tasks will be consistent across all ages of participants. Infants and parents will complete the same EEG and eye-tracking tasks.

#### 4. Describe the Informed Consent Process.

- Upon arrival at the laboratory, participant families are greeted by the experimenter and the study methods and procedure are explained to the parent(s). The consent form is explained to the parent(s) by the experimenter. The parent is then given time to read over the consent forms and ask any

questions that they might have. Once all questions have been answered, the participant's parent and the researcher will sign the infant and parent consent form and the participant family will be offered a copy. All participants will be reminded that they can stop participating at any time and that several breaks will be offered. The potential risk of identification of participants will be explained to parents and parents will be given the option to have their video data excluded for data sharing purposes.

---

## **5. Describe the Data You Will Collect:**

- Adult and infant participants will participate in a study involving eye-tracking and electrophysiological methods. Data will include: questionnaire data, electrophysiological data (EEG recordings), video and audio recordings of parent and infant behaviors, and visual fixation eye-tracking data from both parent and infant. For the questionnaires, demographic information including race, ethnicity and gender will be collected. All data (e.g., computerized files of recordings and responses, demographic information) will be kept confidential to the extent provided by law and will be maintained confidentially on a password protected and encrypted computer in a locked room.

---

